6.2 Data Security

The REDCap server is password-protected, stored under the Robert Wood Johnson Medical School domain, with access limited to only study members. Data will be kept on REDCap for 6 years after which it will be deleted from REDCap. Subject data will be assigned a unique numerical code by REDCap. The study team will be trained no these practices and will be overseen by the PI, [name].

6.3 Data and Safety Monitoring

A. Data/Safety Monitoring Plan

Data will be periodically monitored by the study coordinator to ensure proper data collection and patient safety. Any complaints/concerns will be reported to the study coordinator and immediately addressed. Reports of significant issues will be reported to the IRB by the study coordinator/PI.

B. Data/Safety Monitoring Board Details

N/A

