1.6 Study Variables

A. Independent Variables, Interventions, or Predictor Variables

The independent variables of this study are the use of traditional physical therapy and the use of traditional therapy with BFR therapy.

B. Dependent Variables or Outcome Measures

Outcome measures recorded for this study include: muscle strength, muscle endurance, shoulder range of motion, and qDASH score.

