1.10 Timetable/Schedule of Events

	Before Surgery	Surgery	Week 6 of PT	Week 14 of PT
Demographics	x			
Range of Motion (degrees)			x	x
Muscle Strength (kg)			x	x
Muscle Endurance			x	x
qDASH score			x	x

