4.7 Risks of Harm/Potential for Benefits to Subjects

A. Description of Risks of Harm to Subjects

▪ **Reasonably Foreseeable Risks of Harm**

The use of blood flow restriction therapy carries a risk of developing late-onset muscle soreness, numbness, dizziness, and developing bruises under where the cuff for the tourniquet is placed. Muscle breakdown has also been reported in 0.008% of cases. (1)

▪ **Risk of Harm from an Intervention on a Subject with an Existing Condition**

N/A

▪ **Other Foreseeable Risks of Harm**

Data collected will be stored on REDCap. If these sources were to be breached, there is a risk of losing confidentiality for the subject.

▪ **Observation and Sensitive Information**

N/A

B. Procedures which Risk Harm to Embryo, Fetus, and/or Pregnant Subjects

N/A

C. Risks of Harm to Non-Subjects

N/A

D. Assessment of Social Behavior Considerations

N/A

E. Minimizing Risks of Harm

All paper documents containing data will be shredded by team members after recording the data points to REDCap. Access to REDCap will be limited to study member only and will be password protected. When it comes time for data analysis, the dataset will be exported from REDCap with the option to exclude any identifying material.

▪ Certificate of Confidentiality

N/A

▪ Provisions to Protect the Privacy Interests of Subjects

The subjects will only provide information to providers that they would by default provide information to at this institution, such as physicians and medical students regardless of whether they are participating in this study or not.

F. Potential Direct Benefits to Subjects

There are no direct benefits to subjects from their participation in this research.

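### Section 6.3 promises safety monitoring of the data, but the listed data hold no harm variable, so harms foreseen in section 4.7 are not ascertained systematically or comparably by arm

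*Protocol*

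**What the plan says.** Section 6.3 sets out three steps.

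- Review: "Data will be periodically monitored by the study coordinator to ensure proper data collection and patient safety". No interval is given and the items to be reviewed are not named.
- Complaints: "Any complaints/concerns will be reported to the study coordinator and immediately addressed".
- Escalation: "Reports of significant issues will be reported to the IRB by the study coordinator/PI". What counts as significant is not defined.

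A monitoring board is marked as not applicable.

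Section 4.7 lists what blood flow restriction (BFR) may cause: "late-onset muscle soreness, numbness, dizziness, and developing bruises under where the cuff for the tourniquet is placed". It adds: "Muscle breakdown has also been reported in 0.008% of cases".

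Section 1.6 fixes what is recorded: "Outcome measures recorded for this study include: muscle strength, muscle endurance, shoulder range of motion, and qDASH score". The endpoints in section 1.3, the data collection in section 1.9 and the schedule in section 1.10 agree with that list. They add only demographics and identifiers and the date of surgery. The functional measures and qDASH are taken at weeks 6 and 14 of physical therapy, and section 1.9 places all data collection in REDCap.

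**The concern.** Section 6.3 gives the data a safety purpose that the listed data cannot serve. A coordinator who follows the protocol would be reviewing four efficacy measures taken at two time points. None of them records numbness, dizziness, bruising, soreness or muscle breakdown.

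Harms therefore reach the study only if someone raises them. The protocol does not say that such reports are logged, dated, graded or tied to study arm. No blinding is described and the cuff is used in one arm only, so the readiness to report or notice an event may differ between arms for reasons other than true harm.

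At stake is what the trial can say about harms. Section 1.2 notes that BFR after surgery is not well described for the upper extremity, section 1.4 reports no pilot data, and section 6.4 plans publication. A statement that no adverse events occurred could not be told apart from one in which patients were never asked.

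This cannot be left to a statistical analysis plan. Which harms are asked about, when and on which form is data collection, and an analysis plan cannot recover a variable that was not collected.

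**Working it through.** **Comparison of sections.** No calculation decides the point; it rests on comparing what is to be monitored with what is recorded.

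| Section | What it lists | Harm item? |
|---|---|---|
| 1.3 Endpoints | Strength, endurance, range of motion, qDASH | None |
| 1.6 Outcome measures | The same four | None |
| 1.9 Data collection | Identifiers, date of surgery, the same four | None |
| 1.10 Schedule | Demographics, the same four at weeks 6 and 14 | None |
| 4.7 Risks | Soreness, numbness, dizziness, bruising, muscle breakdown | Named, not recorded |
| 6.3 Monitoring | Review of data for safety; complaints; IRB | Passive route only |

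Section 1.9 describes qDASH as a questionnaire on how upper-extremity disability affects quality of life. On that description it does not replace the section 4.7 list.

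**Inputs for scale.** The protocol gives no figure for harm capture to reproduce. The total of 26 is in sections 1.5 and 4.3. It cannot be rederived, because no error rate, power, effect size or standard deviation is stated, and the point does not depend on it. The allocation ratio is not stated. Assuming 1:1, each arm has 26 / 2 = 13 patients; 10 and 16 are shown as a range.

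**What zero events would exclude with full capture.** Solving (1 − p)^n = 0.05 gives p = 1 − 0.05^(1/n):

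- n = 10: 25.9%
- n = 13: 20.6%
- n = 16: 17.1%

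**What incomplete capture could do (illustration only).** Let r be the true share of BFR patients with a listed harm and c the share of those events that is recorded. With 13 independent patients, P(none recorded) = (1 − r × c)^13. Both r and c are assumptions.

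| r | c = 25% | c = 50% | c = 100% |
|---|---|---|---|
| 10% | 0.975^13 = 72% | 0.95^13 = 51% | 0.90^13 = 25% |
| 20% | 0.95^13 = 51% | 0.90^13 = 25% | 0.80^13 = 5.5% |

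An empty harms record is thus more likely when capture is poor. At r = 10% it would still occur a quarter of the time with every patient asked.

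**Muscle breakdown.** At the 0.008% in section 4.7, read as a rate per patient (the unit is not stated), the chance of at least one case in 13 is 1 − (1 − 0.00008)^13 = 0.10%. A checklist will tell nothing useful about the frequency of this harm. Its value lies with the commoner ones.

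**The case against.** The strongest reply is that section 6.3 should be read as a whole. It never says that adverse events sit in the outcome dataset. Complaints and IRB reporting supply the safety route, the therapists have formal BFR training (section 2.2), and BFR sessions take place twice a week (section 1.3), so an observed bruise or dizzy spell can be raised. On this reading only detail is missing.

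Much of this stands, and it rules out several stronger readings that a reader might infer.

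- That the monitoring cannot work at all. The complaint and IRB steps exist and can catch volunteered or observed events.
- That harms could never be reported by arm. Complaints could be counted by arm if they were logged; no log is specified, and the counts would not be comparable.
- That complaints must be unprompted or come only from patients. Section 6.3 sets no such limit.
- That no safety data are collected. The supported statement is that none is listed: the REDCap forms are not shown, and parts of the document were not available for this check.
- That the aim in section 1.1 fails without harms data. It defines utility as improvement in strength and claims no safety objective.
- That the cuff goes on a freshly repaired shoulder. Section 1.1 places the comparison in phase two of rehabilitation.

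It is also fair that the capture probabilities are assumed and that 13 patients say little about harm rates even with perfect ascertainment.

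What does not stand is that only detail is missing. The protocol fixes the data items consistently in four places, assigns a safety purpose to reviewing the data, and leaves harms to a passive route. Followed exactly, it gives incomplete harms data that cannot be compared between arms.

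**Conclusion.** The concern holds in limited form. The data listed for collection contain no harm variable, so the data review in section 6.3 cannot detect the harms foreseen in section 4.7. The complaint and IRB route is a partial safeguard for serious events, not a means of ascertaining harms equally in both arms. A finding of no adverse events could reflect not asking.

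The conclusion rests on the lists in sections 1.3, 1.6, 1.9 and 1.10 being complete and on no blinding being described. It does not rest on the capture probabilities, which only illustrate the effect. The one figure worth carrying into a report is the limit on what zero events can show: about 21% one-sided 95% for 13 patients, or 17% to 26% for 16 down to 10.

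This should be changed before enrolment. It does not affect the validity of the strength, endurance, range-of-motion or qDASH comparisons.

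**What to change.** - Add an adverse-event row to table 1.10 and a brief checklist to the REDCap forms in section 1.9, completed at existing physical therapy visits in both arms with the same questions.
- Cover soreness, numbness, dizziness, arm bruising, suspected muscle breakdown and any other adverse event. Asking about arm bruising, rather than bruising under a cuff, keeps the item answerable in the control arm.
- Record cuff-specific items, such as an interrupted BFR session, in the BFR arm only, and keep them out of the between-arm comparison.
- Name this form in section 6.3 as the data that the coordinator reviews, and define which events count as significant for IRB reporting.
- Report counts by arm descriptively, without a test, and state the upper limit that applies when no events are seen.

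The cost is one short form and a small data-entry burden, with no extra visits, staff or procedures. The change concerns data capture only; no treatment or stopping rule is proposed.

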6.4 Reporting Results

A. Individual Subjects' Results

N/A

B. Aggregate Results

Aggregate research will not be shared with subjects.

C. Professional Reporting

Once recruitment has ended and data analysis is done, findings are expected to be organized into abstracts and manuscripts for presentation and publication to medical journals and medical societies.

D. Clinical Trials Registration, Results Reporting and Consent Posting

Clinical trial registry in process.

6.5 Secondary Use of the Data

N/A

7.0 Research Repositories – Specimens and/or Data

N/A

8.0 Approvals/Authorizations

N/A

